10.1.3.7.	Counting rules for combining solicited and unsolicited adverse events	14
10.1.3.8.	Counting rules for occurrences of solicited adverse events	16
10.1.4.	Display of decimals.....	16
10.1.4.1.	Percentages	16
10.1.4.2.	Demographic/baseline characteristics statistics	16
10.1.5.	Statistical methodology	16
10.1.5.1.	Exact confidence intervals around proportions	16
10.2.	TFL ToC	16
11.	REFERENCES.....	17

CONFIDENTIAL

208236 (ROTA-096)

Statistical Analysis Plan Amendment 1

[figure not shown]
LIST OF ABBREVIATIONS

AE	Adverse event
CI	Confidence Interval
CRF	Case Report Form
CSR	Clinical Study Report
CTRS	Clinical Trial Registry Summary
ES	Exposed Set
eTMF	Electronic Trial Master File
GSK	GlaxoSmithKline
LL	Lower Limit of the confidence interval
MedDRA	Medical Dictionary for Regulatory Activities
NA	Not Applicable
SAE	Serious adverse event
SAP	Statistical Analysis Plan
SBIR	GSK Biological's Internet Randomisation System
SD	Standard Deviation
SDTM	Study Data Tabulation Model
SR	Study Report
TFL	Tables Figures and Listings
ToC	Table of Content
UL	Upper Limit of the confidence interval

CONFIDENTIAL208236 (ROTA-096)
Statistical Analysis Plan Amendment 1**1. DOCUMENT HISTORY**

Date	Description	Protocol Version
11 June 2019	First version	Final version 2: 09 November 2018
15 October 2020	Amendment 1*	Final version 2: 09 November 2018

* following CBER request to comply with the CDISC Vaccines Therapeutic Area guide, the SDTM have been updated. One of the updates requires that solicited events which continue beyond the observation period be stored in the Adverse Events (AE) domain. This amendment aims at clarifying that these solicited events will not be included in the summaries of unsolicited adverse events. Some summaries will be generated according to whether Number and percentage of subjects vaccinated, completed and withdrawn from the study with reason for study withdrawal – subjects receiving their first dose on or before October 31st 2019

2. STUDY DESIGN**Figure 1 Study design overview**

The Extended safety follow-up (ESFU) contact (by telephone call or any other convenient procedure) will take place 6 months after the last dose of the study vaccines.

N=Target number of subjects, n=Target number of subjects in each study group.

*Two doses of the study vaccines will be administered to subjects at 1-month or 2-months interval.

An Independent Data Monitoring Committee (IDMC) consisting of clinical experts and a biostatistician will review the safety data on a regular basis to evaluate if there is any safety concern with the PCV-free liquid HRV vaccine.

CONFIDENTIAL

208236 (ROTA-096)
 Statistical Analysis Plan Amendment 1

Table 1 Study groups, treatments and epoch foreseen in the study

Study groups	Number of subjects	Age at Dose 1 (Min-Max)	Treatment name	Vaccine/Product names
Liq	675	6-12 weeks	HRV Liquid (oral administration)	HRV PCV-free
Lyo	675	6-12 weeks	HRV Lyophilized (oral administration)	HRV Lyo
				HRV Diluent

- Control: active control, GSK's lyophilized HRV vaccine.
- Vaccination schedule:
 - Two doses of HRV vaccines to be administered according to 0, 1-2-month schedule.
 - Concomitant administration of routine childhood vaccines will be allowed according to the local immunization practices in each participating country.
- Treatment allocation: Randomized with balanced allocation (1:1) using GSK's central internet randomization system (SBIR). Refer to Section 7.2.2.2 of the protocol for a detailed description of the randomization method.
- Blinding: observer-blind.

The following group names will be used in the TFLs:

Group order in tables	Group label in tables	Group definition for footnote
1	Liq	HRV vaccine liquid formulation
2	Lyo	HRV vaccine lyophilised formulation

CONFIDENTIAL208236 (ROTA-096)
Statistical Analysis Plan Amendment 1

3. OBJECTIVES/ENDPOINTS

Table 2 Study objectives and endpoints

Objectives	Endpoints
Primary	
To evaluate the reactogenicity of the liquid HRV vaccine and lyophilized HRV vaccine in terms of solicited adverse events (AEs) during the 8-day (Day 1–Day 8) follow-up period after each vaccination.	
 Occurrence of each solicited general AE within 8 days (Day 1–Day 8) after each vaccination.
To assess the safety of the liquid HRV vaccine and lyophilized HRV vaccine in terms of unsolicited AEs during the 31-day (Day 1–Day 31) follow-up period after each vaccination and serious adverse events (SAEs) during the entire study period.	
 Occurrence of unsolicited AEs within 31 days (Day 1–Day 31) after any vaccination, according to the medical dictionary for regulatory activities (MedDRA) classification. Occurrence of SAEs throughout the study period (i.e. from Dose 1 of the HRV vaccine to study conclusion at the end of the follow-up period).

4. ANALYSIS SETS

4.1. Definition

The following analysis sets will be used for this study:

Analysis set	Description
Enrolled	All subjects who were randomised or vaccinated
Exposed	All subjects who received at least 1 dose of the study treatment. For the sake of analysis, the study group is defined by the treatment administered at Dose 1.

4.2. Criteria for eliminating data from Analysis Sets

Elimination codes are used to identify subjects to be eliminated from analysis. Detail is provided below for each set.

4.2.1. Elimination from Enrolled Set

Only subjects with codes 800 and 900 (invalid informed consent or fraudulent data) will be eliminated from the Enrolled Set.

4.2.2. Elimination from Exposed Set

All subjects with code 1030 (Study vaccine not administered at all) or codes 800 or 900 (invalid informed consent or fraudulent data) will be eliminated from the Exposed Set.

5. STATISTICAL ANALYSES

Note that standard data derivation rules and statistical methods are described in Section 10.1 and will not be repeated here. The study specific data derivation rules and statistical methods will be described in section 9.

CONFIDENTIAL208236 (ROTA-096)
Statistical Analysis Plan Amendment 1**5.1. Important protocol deviations**

The following deviations will be considered important protocol deviations. Only codes 800, 900, and 1030 will lead to elimination from analysis sets (see section [4.2](#)).

Code	Decode: Condition under which the code is used
800	Fraudulent data
900	Invalid informed consent
1030	Study vaccine dose not administered but subject number allocated: subjects enrolled but not vaccinated
1050	Randomisation failure: forced or manual randomization*. First dose of vaccine administration not aligned with the randomized treatment.
1040	Administration of concomitant vaccine(s) forbidden in the protocol: Administration of a non study HRV vaccine or non routine vaccine starting from 30 days before the first vaccination up to study end.
1060	Randomisation code broken at the investigator site: Subjects unblinded in the central randomization system or unblinding reported as protocol deviation
1070	Study vaccine dose not administered according to protocol: 
 Subjects vaccinated with the correct vaccine but who regurgitated for one of the 2 doses and did not receive a vaccine replacement; subjects for whom the second administered dose is not aligned with the first dose (e.g. lyo as second dose after a first dose with liquid) Subject who did not receive the second dose Route of vaccination which is not oral
1080	Vaccine temperature deviation: Subjects who have received a vaccine which had a temperature deviation qualified as inappropriate for use by Quality Assurance.
1090	Expired vaccine administered: Subjects who received an expired vaccine
2010	Protocol violation linked to the inclusion/exclusion criteria: Ineligible subjects who was vaccinated (i.e. Age at dose 1 is not between 42-90 days, gestational age is < 29 weeks or other eligibility criteria – see section 6.1 of the protocol)
2040	Administration of any medication forbidden by the protocol: administration of 
 Any investigational or non-registered drug between Visit 1 to Visit 3. Immunosuppressants or other immune-modifying drugs administered chronically (i.e., more than 14 days) during the study period between Visit 1 to Visit 3. For corticosteroids, this will mean prednisone (0.5 mg/kg/day, or equivalent). Immunoglobulins and/or any blood products administered during the study period between Visit 1 to Visit 3. Long-acting immune-modifying drugs administered at any time during the study period (e.g., infliximab).
2080	Non-compliance with vaccination schedule (including wrong and unknown dates): Subjects who did not comply with the interval for dose 2 (Dose 2 should be between 28-83 days after Dose 1).
2500	Short follow-up: subjects with a safety follow-up period after the last dose of HRV vaccine that is less than 180 days.
2600	Subject did not provide any post-vaccination solicited safety data: Vaccinated subjects without complete documentation of solicited symptoms i.e. for a vaccine dose administered, at least one solicited symptom is not documented as being present or absent.

* Forced randomization: In case of supplies shortage for the next assigned vaccine according to the randomization schedule at the clinical site, the randomization system will use the forced randomization procedure in order to continue to enrol and vaccinate subjects. The system moves seamlessly to the next treatment/randomization number for which vaccine supplies are available. The site will not be aware of the forced randomization event.

CONFIDENTIAL208236 (ROTA-096)
Statistical Analysis Plan Amendment 1

Manual randomization: In case the randomization system is unavailable, the investigator has the option to perform randomization by selecting supplies available at the site according to a pre-defined rule. In case the randomization system is available, a vaccine different from the randomized treatment may have been administered at dose 1.

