12.3.3. Solicited adverse events

Solicited general adverse events

The following general AEs will be solicited ([Table 11](#)):

Table 11 Solicited general adverse events

Infants
Fever
Irritability/Fussiness
Diarrhea
Vomiting
Loss of appetite
Cough/runny nose

Note: Parent(s)/LAR(s) will be instructed to measure and record the oral, axillary or rectal body temperature in the evening. Should additional temperature measurements be performed at other times of day, parent(s)/LAR(s) will be instructed to record the highest temperature in the diary card.

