5.2. Demography

5.2.1. Analysis of demographics/baseline characteristics planned in the protocol

The median, mean, range and standard deviation of age (in weeks) at each study vaccine dose and of the gestational age at birth will be computed by study group. The median, mean and standard deviation of length (in centimetres) and weight (in kilograms) at Visit 1 will be computed by study group. The distribution of racial and sex composition of the study population will be presented.

The distribution of subjects enrolled in each country/site will be tabulated across and per study group.

Important protocol deviations (as defined in section 5.1) will be tabulated by study group.

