10.1.2.2. Daily recording of solicited AEs

When a specific solicited AE is marked as having not occurred following a specific vaccination (i.e. SDTM CE.CEOCCUR=N for the specified post-vaccination period for the solicited AE in question), all daily measurements will be imputed as Grade 0.

When a specific solicited AE is marked as having occurred following a specific vaccination (i.e. SDTM CE.CEOCCUR=Y for the specified post-vaccination period for the solicited AE in question), any missing daily recordings will be given imputed values to allow them to contribute to the 'Any' rows but not to specific grade rows of the solicited AE summary tables.

When the occurrence of a specific solicited AE is not present (i.e. SDTM CE.CEOCCUR is neither Y nor N for the specified post-vaccination period for the solicited AE in question) but the group of solicited AEs is marked as having occurred (i.e. SDTM CE.CEOCCUR=Y), all missing daily recordings will be given imputed values to allow them to contribute to the 'Any' rows but not to specific grade rows of the solicited AE summary tables.

The following table shows how subjects contribute to each category for a specific solicited AE over the Day X to Day Y post-vaccination period:

Solicited AE category	Subjects included in the calculation of the numerator
Any	All subjects with at least 1 occurrence of the solicited AE at grade 1, grade 2, or grade 3 between Day X and Day Y or with the solicited AE marked as present and at least 1 missing daily recording between Day X and Day Y
At least grade 1	All subjects with at least 1 occurrence of the solicited AE at grade 1, grade 2, or grade 3 between Day X and Day Y
At least grade 2	All subjects with at least 1 occurrence of the solicited AE at grade 2 or grade 3 between Day X and Day Y
At least grade 3	All subjects with at least 1 occurrence of the solicited AE at grade 3 between Day X and Day Y

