10.2. TFL ToC

A TFL ToC detailing the tables, figures, and listings that will be produced will be provided separately.

CONFIDENTIAL

208236 (ROTA-096)
Statistical Analysis Plan Amendment 1

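### Do the loosely worded deviation codes 2600, 1070 and 1040 in SAP 5.1 call for a change to the plan?

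*SAP*

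**What the plan says.** SAP 5.1 lists the important protocol deviations, each with a code, a short label and a condition. Three are at issue.

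- **Code 2600** reads "Subject did not provide any post-vaccination solicited safety data: Vaccinated subjects without complete documentation of solicited symptoms". The condition then says that, for a dose that was given, "at least one solicited symptom is not documented as being present or absent".
- **Code 1070** is labelled "Study vaccine dose not administered according to protocol". It has four conditions: regurgitation without a replacement dose, a second dose of the other product, no second dose, and a non-oral route.
- **Code 1040** is labelled as a concomitant vaccine that the protocol forbids. It covers a non-study rotavirus vaccine or a non-routine vaccine, from 30 days before the first dose to the end of the study.

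SAP 5.2.1 gives the use of these codes: "Important protocol deviations (as defined in section 5.1) will be tabulated by study group". SAP 4.2 and 5.1 confine elimination from the analysis sets to codes 800, 900 and 1030. SAP 5.4.1 places the primary safety analysis on the Exposed Set, and SAP 6 states that all analyses are descriptive. Table layout is left to another document (SAP 10.2): "A TFL ToC detailing the tables, figures, and listings that will be produced will be provided separately".

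**The concern.** Read literally, the deviation table could misstate how the trial was run.

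- Under code 2600, an infant with almost complete diary cards could be reported as having given no solicited data. The same infant might still feed the solicited tables. SAP 10.1.2.2 covers the case where a symptom has no yes/no answer "but the group of solicited AEs is marked as having occurred", and says "all missing daily recordings will be given imputed values to allow them to contribute to the" 'Any' rows.
- Under code 1070, site staff who followed protocol 7.1 or 7.6 could be shown as having departed from the protocol, on the same line as true misadministration.
- Under code 1040, a licensed vaccine given after the 6.2.2 window had closed could be counted as forbidden.

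Readers judge trial conduct and diary completeness from this table, so an inflated or mislabelled count could lower confidence in the data, or suggest a difference in conduct between the groups.

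**Working it through.** The plan states no expected deviation counts, so there is no figure to reproduce. The check compares the texts and then traces where the codes are used.

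**1. Code 2600.** Protocol 12.3.3 ("The following general AEs will be solicited") lists six events in Table 11, and Table 5 gives two doses.

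- Items per two-dose infant: 6 × 2 = 12.
- One item missing: 11/12 = 91.7% documented. After a single dose: 5/6 = 83.3%.

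The documents give no missingness rate. As an illustration only, suppose each item is missing independently with probability q. The share coded is then 1 − (1 − q)^12:

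| q (assumed) | Share coded | Infants of 675 |
|---|---|---|
| 0.1% | 1.2% | 8 |
| 0.5% | 5.8% | 39 |
| 1% | 11.4% | 77 |
| 2% | 21.5% | 145 |

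Under independence almost no infant has all 12 items missing (q^12), so the label would be wrong for nearly everyone coded. In practice gaps cluster, since a lost diary card removes every item for that dose. For the same q, clustering lowers the number coded and raises the share with no data at all. The table is therefore an upper guide.

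**2. Code 1070.** Set against the protocol:

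| SAP condition | Protocol position |
|---|---|
| Regurgitation, no replacement | 7.1 makes replacement optional, for events within 30 minutes that may have impaired take, at the investigator's discretion |
| No second dose | 7.6 directs that some infants receive no further dose |
| Second dose of the other product | A departure from the allocated treatment |
| Non-oral route | A departure from Table 5 |

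Two of the four conditions can include conduct that the protocol permits or directs. For regurgitation, assume a fraction r of doses is affected and a fraction s of those is not replaced, with doses independent. Infants coded per group are 675 × [1 − (1 − rs)²]. With r = 1% and s = 25% this is 675 × (1 − 0.9975²) = 3.4. With r = 5% and s = 75% it is 675 × (1 − 0.9625²) = 49.7. Both rates are assumptions.

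**3. Code 1040.** The final safety contact is 180 to 210 days after Dose 2 (protocol Table 2).

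- Nominal excess over the 6.2.2 limit: 180 − 30 = 150 to 210 − 30 = 180 days.
- If routine recording stops at Visit 3 (7.5.1), which falls 31 to 83 days after Dose 2: 31 − 30 = 1 to 83 − 30 = 53 days.

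The schedule of activities, however, says that all concomitant vaccinations in the study period are recorded. The excess that would be captured is therefore not settled. The content is narrow in either case. Section 6.2.2 exempts licensed routine childhood vaccines and inactivated influenza vaccine, and its separate bar on investigational or non-registered products already covers the study period. What remains is mainly licensed non-routine vaccines given late.

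**4. Where the codes are used.** None of the three is among the elimination codes, so the Enrolled and Exposed Sets are unchanged. The rules in SAP 10.1.2.2 for missing solicited data work from the diary records, not from deviation codes. The change in any planned percentage or confidence interval is 0.

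**The case for a change.** The strongest case for acting is that a definition in a SAP should be right whatever its consequence, and that mending it costs a few words. Protocol 10.3.2 describes important deviations as including misadministration and prohibited vaccination; conduct that the protocol allows is neither, and SAP 8 declares no departure from the planned analyses. The two products also differ in volume (1.5 ml and 1 ml in Table 5). Unreplaced regurgitation could therefore differ by group, and an imbalance in code 1070 could be taken for poorer conduct.

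The wording criticism stands, above all for code 2600, where label and condition disagree within one entry. Several things limit the rest.

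- The condition in code 2600 is determinate. A programmer applies it without having to guess; only the label misleads.
- A missed second dose departs from the planned two-dose course, so listing it is a reporting convention. Full-course completion is described by group anyway (SAP 5.3.1), and the reason is recorded under protocol 9.2.
- Regurgitation and replacement doses are recorded in the eCRF, so an imbalance in code 1070 can be traced to its source.
- A finer split could be only partial. The documents show no field for impaired take or for the time of regurgitation, and the five reasons in 9.2 do not map one-to-one to 7.6.
- The link to the 'Any' rows is uncertain. The numerator table in SAP 10.1.2.2 requires the event to be marked as present, which a symptom with no answer is not. Code 2600 plays no part on either reading.

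Nor does code 2080 add to the case. Its 28-83 day interval matches protocol Table 2, and protocol 10.3.2 names departures from that interval as important deviations. A later dose given under the 24-week footnote can properly still be counted as outside the interval.

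**Conclusion.** No change to the plan follows. Code 2600 carries a clerical slip in its label. Code 1070 groups unlike events under one heading, which is a common trade-off in a deviation list. Code 1040 has a window that differs from protocol 6.2.2. That window, and the recording periods in 7.5.1 and the schedule of activities, do not agree, and the sponsor must reconcile them as housekeeping; this note does not choose between them.

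The effect is confined to labels and counts in one descriptive table. Its size is zero for analysis sets, safety percentages, confidence intervals and the safety conclusion. The number of infants labelled too harshly cannot be derived from the documents; the illustrative ranges above rest on assumed rates and on independence. An analyst can apply the written conditions, title the 2600 line as incomplete solicited data, and footnote what 1070 and 1040 include. The conclusion assumes that the separate table shells give these codes no further role; nothing in the protocol or SAP suggests that they do.

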5.2. Demography

5.2.1. Analysis of demographics/baseline characteristics planned in the protocol

The median, mean, range and standard deviation of age (in weeks) at each study vaccine dose and of the gestational age at birth will be computed by study group. The median, mean and standard deviation of length (in centimetres) and weight (in kilograms) at Visit 1 will be computed by study group. The distribution of racial and sex composition of the study population will be presented.

The distribution of subjects enrolled in each country/site will be tabulated across and per study group.

Important protocol deviations (as defined in section 5.1) will be tabulated by study group.

5.2.2. Additional considerations

None

5.3. Exposure

5.3.1. Analysis of exposure planned in the protocol

Number of enrolled, vaccinated (at least 1 vaccination, full vaccination course) subjects and reason for withdrawal, included in each study group and in total will be described.

5.3.2. Additional considerations

None

5.4. Analysis of safety and reactogenicity

5.4.1. Analysis of safety and reactogenicity planned in the protocol

The primary safety analysis will be performed on the Exposed set.

The percentage of doses and of subjects reporting at least 1 AE (solicited or unsolicited) during the 8-day (Day 1-Day 8) solicited follow-up period post-vaccination will be computed, along with exact 95% CI. The same calculations will be done for AEs (solicited or unsolicited) rated as grade 3 in intensity, those assessed as causally related to vaccination, those rated as grade 3 in intensity with causal relationship to vaccination and those that resulted in a medically attended visit.

CONFIDENTIAL208236 (ROTA-096)
Statistical Analysis Plan Amendment 1

The percentage of doses and of subjects reporting each individual solicited general AE will be computed, over the 8-day (Day 1-Day 8) solicited follow-up period post-vaccination, along with exact 95% CI. The same calculations will be done for each individual general solicited AE rated as grade 3 in intensity, those assessed as causally related to vaccination, those rated as grade 3 in intensity with causal relationship to vaccination and those that resulted in a medically attended visit. For fever, additional analyses will be performed by 0.5°C increments. These calculations will also be performed by country, sex and frequent race.

The verbatim reports of unsolicited AEs will be reviewed by a physician and the signs and symptoms will be coded according to MedDRA. Every verbatim term will be matched with the appropriate preferred term. The percentage of subjects with unsolicited AEs occurring within 31-day (Day 1-Day 31) follow-up period after any dose with its exact 95% CI will be tabulated by group, and by preferred term. Similar tabulation will be done for unsolicited AEs rated as grade 3, for unsolicited AEs with causal relationship to vaccination, for unsolicited AEs rated as grade 3 with causal relationship to vaccination and those that resulted in a medically attended visit. These calculations will also be performed by country.

For each study group, the percentage of subjects who started taking at least 1 concomitant medication, antipyretic medication and prophylactic antipyretic medication during the 8-day (Day 1-Day 8) and 31-day (Day 1-Day 31) follow-up periods post-vaccination will be tabulated by dose, by subject for each dose and across the 2 doses.

Subjects who experienced at least 1 SAE during the entire study period (from Dose 1 till ESFU contact at Month 7-8) will be summarised by study group and all SAEs will be tabulated.

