10. STATISTICAL CONSIDERATIONS

10.1. Sample size determination

The target sample size is 1350 subjects (675 subjects per group).

Table 10 provides the 95% exact CI for different possible observed number of subjects with AEs for the study (675 subjects per group).

Table 10 Two-sided 95% exact confidence intervals for the true adverse event rate at different possible observed adverse event rates (675 subjects per group)

Subjects vaccinated	Observed number subjects reporting the adverse events	Observed percentage of subjects with the adverse events	95% exact confidence interval	
			Lower limit	Upper limit
675	0	0.0	0.0%	0.5%
	1	0.1	0.0%	0.7%
	10	1.5	0.7%	2.7%
	30	4.4	3.0%	6.2%
	50	7.4	5.5%	9.6%
	100	14.8	12.2%	17.7%

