10.3.3. Safety analyses

The primary safety analysis will be performed on the Exposed set.

Endpoint	Statistical analysis methods
Primary	
Within groups assessment
 
The percentage of doses and of subjects reporting at least 1 AE (solicited or unsolicited) during the 8-day (Day 1-Day 8) solicited follow-up period post-vaccination will be computed, along with exact 95% CI. The same calculations will be done for AEs (solicited or unsolicited) rated as grade 3 in intensity, those assessed as causally related to vaccination, those rated as grade 3 in intensity with causal relationship to vaccination and those that resulted in a medically attended visit.
 
The percentage of doses and of subjects reporting each individual solicited general AE will be computed, over the 8-day (Day 1-Day 8) solicited follow-up period post-vaccination, along with exact 95% CI. The same calculations will be done for each individual general solicited AE rated as grade 3 in intensity, those assessed as causally related to vaccination, those rated as grade 3 in intensity with causal relationship to vaccination and those that resulted in a medically attended visit. For fever, additional analyses will be performed by 0.5°C increments. These calculations will also be performed by country, sex and frequent race.
 
The verbatim reports of unsolicited AEs will be reviewed by a physician and the signs and symptoms will be coded according to MedDRA. Every verbatim term will be matched with the appropriate preferred term. The percentage of subjects with unsolicited AEs occurring within 31-day (Day 1-Day 31) follow-up period after any dose with its exact 95% CI will be tabulated by group, and by preferred term. Similar tabulation will be done for unsolicited AEs rated as grade 3, for unsolicited AEs with causal relationship to vaccination, for unsolicited AEs rated as grade 3 with causal relationship to vaccination and those that resulted in a medically attended visit. These calculations will also be performed by country.
 
For each study group, the percentage of subjects who started taking at least 1 concomitant medication, antipyretic medication and prophylactic antipyretic medication during the 8-day (Day 1-Day 8) and 31-day (Day 1-Day 31) follow-up periods post-vaccination will be tabulated by dose, by subject for each dose and across the 2 doses.
 
Subjects who experienced at least 1 SAE during the entire study period (from Dose 1 till ESFU contact at Month 7-8) will be summarized by study group and all SAEs will be tabulated.

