5.4.2. Additional considerations

The definition of frequent race is any race (cDISC categories) with at least 40 subjects overall. The 'Other races' subgroup will include all races that do not meet this criterion.

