6. ANALYSIS INTERPRETATION

All analyses are descriptive.

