10.1.5. Statistical methodology**10.1.5.1. Exact confidence intervals around proportions**

The exact confidence intervals around within-group proportions are derived using the method of Clopper and Pearson [[Clopper](#), 1934].

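### The exact 95% CI planned for the percentage of doses treats an infant's two doses as independent, so it covers less than 95% if AEs correlate within infants

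*SAP*

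**What the plan says.** SAP 5.4.1, repeating protocol 10.3.3, plans results on two units, doses and subjects. The first set is "The percentage of doses and of subjects reporting at least 1 AE (solicited or unsolicited) during the 8-day (Day 1-Day 8) solicited follow-up period". The second is "The percentage of doses and of subjects reporting each individual solicited general AE will be computed". Both carry an exact 95% CI and are repeated for grade 3, vaccine-related, grade 3 related and medically attended events. The solicited-AE results are also broken down by country, sex and frequent race.

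SAP 10.1.5.1 supplies one interval method: "The exact confidence intervals around within-group proportions are derived using the method of Clopper and Pearson". On exposure, SAP section 2 states: "Two doses of HRV vaccines to be administered according to 0, 1-2-month schedule". Neither document mentions within-infant correlation, clustering or a robust variance.

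The AE paragraphs do not say whether Dose 1 and Dose 2 share a denominator, and the list of tables is a separate document (SAP 10.2). The medication paragraph of SAP 5.4.1 does separate the levels: its percentages "will be tabulated by dose, by subject for each dose and across the 2 doses".

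**The concern.** Clopper-Pearson guarantees at least 95% coverage only for independent yes/no observations. An infant's two doses share the same child, household and usually the same diary keeper, so an infant with irritability or a runny nose after Dose 1 may well be likelier to report it after Dose 2. Counting 675 infants as 1350 independent doses then overstates the information.

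The resulting interval would be called exact 95% without having that property, and in a safety study the error is in the unwelcome direction because the upper limit is too low. With no events, for example, 0/1350 doses gives an upper limit of 0.3%, against 0.5% for 0/675 subjects in protocol Table 10, although the same infants were observed.

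**Working it through.** **Inputs.** From the documents: 675 infants per group (protocol 10.1), 2 scheduled doses, two-sided 95% Clopper-Pearson. Assumed: ICC of 0.1, 0.3 and 0.5, true AE rates of 2-30% per dose, and both doses pooled.

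**The plan's own figures.** Clopper-Pearson at n = 675 reproduces 10 of the 12 limits in protocol Table 10, which confirms the method. The exceptions are the upper limits for 1 event (0.7% stated, 0.82% computed) and 30 events (6.2% stated, 6.28% computed). They do not bear on this point. Table 10 shows precision per subject only; the documents give no dose-level figure.

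**Variance.** For N infants with two doses each, rate p and correlation ICC:

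- true variance of the pooled percentage: p(1 - p)(1 + ICC)/(2N)
- variance under independence: p(1 - p)/(2N)
- ratio: 1 + ICC

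A normal approximation to the coverage is 2Φ(1.96/√(1 + ICC)) - 1. It gives 93.8%, 91.4% and 89.0% for ICC 0.1, 0.3 and 0.5.

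**Exact coverage.** With q = 1 - p, each infant has 0, 1 or 2 doses with the event, with probabilities q² + ICC·pq, 2pq(1 - ICC) and p² + ICC·pq. Summing over N infants gives the exact distribution of the total. Coverage of Clopper-Pearson on 2N doses was averaged over 201 rates within 15% of each nominal rate, to smooth out discreteness.

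| Infants per group | Rate | ICC 0.1 | ICC 0.3 | ICC 0.5 |
|---|---|---|---|---|
| 675 (full group) | 2% | 95.0% | 92.9% | 90.7% |
| 675 | 10% | 94.4% | 92.1% | 89.8% |
| 675 | 30% | 94.2% | 91.9% | 89.6% |
| 337 (one sex, even split assumed) | 10% | 94.6% | 92.4% | 90.1% |
| 337 | 30% | 94.4% | 92.1% | 89.8% |
| 20 (smallest frequent race, even split assumed) | 2% | 98.8% | 98.0% | 97.3% |
| 20 | 5% | 98.1% | 97.2% | 96.4% |
| 20 | 10% | 96.3% | 94.5% | 92.3% |
| 20 | 30% | 95.8% | 93.8% | 91.7% |

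At ICC 0 the full-group value at a 30% rate is 95.3%. The 20-infant row follows from SAP 5.4.2: "The definition of frequent race is any race (cDISC categories) with at least 40 subjects overall".

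**Width.** Clopper-Pearson on 1350/(1 + ICC) doses, that is 1227, 1038 and 900 effective doses:

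- At 30%, the half-width is 2.48 points as planned, against 2.60, 2.83 and 3.05 (5%, 14% and 23% wider).
- At 14.8%, the rate in the last row of Table 10, the planned pooled interval is 13.0-16.8%, against 12.9-16.9%, 12.7-17.1% and 12.6-17.3%.

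**Robustness.** If 5-10% of infants miss Dose 2, mean coverage at rates of 10-30% is 94.3-94.4%, 92.1-92.2% and 89.8-90.0%. Unequal dose rates matter little: at 35% and 25%, the average of p(1 - p) is (0.2275 + 0.1875)/2 = 0.2075, against 0.2100 at a common 30%, a change of about 1%.

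**The case against.** The strongest reply has three parts.

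- **Pooling is inferred.** No sentence puts both doses in one denominator, and the medication paragraph concerns percentages that carry no CI. This is true, but within a single dose the number of doses equals the number of subjects, so reporting both units would be redundant unless doses are pooled. If the sponsor does not pool, one clarifying sentence closes the point.
- **The loss depends on an unknown ICC.** This stands. At ICC 0.1 coverage is less than one point below nominal for rates of 10-30%, and the documents cannot show which value is realistic.
- **Little hangs on it.** SAP section 6 states: "All analyses are descriptive". There is no test, margin or decision rule, and valid per-subject intervals come from the same sentence. At a 14.8% rate the limits move by less than half a point even at ICC 0.5. This also stands, and it limits the importance. It does not make the interval exact.

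A footnote saying that doses are treated as independent would be a lighter remedy. It would warn the reader but leave an interval labelled 95% that may cover about 90%.

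**Conclusion.** The plan is wrong as written and should be corrected, though the consequence is modest. On the pooled reading, and with positive within-infant correlation, the full-group interval for the percentage of doses falls short of 95%: slightly at ICC 0.1, by about 3 points at 0.3 and by about 5 points at 0.5, for rates of 10-30%. At a 2% rate the built-in conservatism of Clopper-Pearson offsets an ICC only up to about 0.1.

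Sex subgroups behave like the full group. In the smallest race subgroups, uncommon events (2-5%) stay above 95%, and a shortfall appears only at rates of about 10% or more with an ICC of about 0.3 or higher.

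Per-subject, Dose 1-only and Dose 2-only intervals are unaffected, as are the sample size and all point estimates. The calculation is firm given its conditions; the ICC values and the pooling are assumptions.

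**What to change.** In SAP 10.1.5.1, limit Clopper-Pearson to per-subject and single-dose percentages. For percentages pooled over doses, choose one option:

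1. **Report the percentage without a CI.** This is the simplest choice, needs no ICC and suits small subgroups best.
2. **Use Clopper-Pearson on doses/(1 + estimated ICC), with the ICC floored at 0.** When events are too few to estimate the ICC (for example fewer than 10 doses with the event), use the number of subjects as the effective sample size. With zero events the upper limit is then 0.5%, as in the 0/675 row of Table 10.

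In simulation with 675 infants and ICC 0-0.5, option 2 gave coverage of 95.3-95.6% at rates of 10-30%, 95.9-96.3% at 2% and 98.3-98.4% at 0.5%, where the fallback was used in 81-85% of trials.

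Either option departs from the exact CI in protocol 10.3.3, so it should be entered in SAP section 8, which now lists no changes.

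The cost is one sentence, one section 8 entry and minor programming. Under option 2, full-group intervals widen by about 5-23% at rates of 10-30% for ICC 0.1-0.5, and by about 40-45% at a 0.5% rate. In a 20-infant subgroup the fallback can widen already conservative intervals by 50-80%.
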